9.3.2 Concomitant Medications, Concomitant Procedures and Surgical Therapy

Prior medications are defined as medications with a start date before the first initiation of study medication. Concomitant medications are defined as medications which:

- Started after the initiation of study medication,
- Had a stop date on or after the first administration of study medication, or
- Are ongoing on Day 15.

It is possible for a medication to be both prior and concomitant. It should be noted that medications administered to or taken by the subject during the study will only be recorded from the time of informed consent through to Day 15 of the study.

Medications with partial start dates will be determined as prior and/or concomitant medications by using available non-missing information. Medications with completely missing start dates (i.e. missing information for medication start day, month, and year) will be assumed to be concomitant. If just the day is missing, and the month and year are the same as the month and year of study drug administration, the medication will be considered concomitant. If the day and month are missing and the year is present, and is the same as the year of study drug administration, the medication will be considered concomitant.

Medications will be coded using the WHO (World Health Organization) Drug Dictionary March 2010 version international thesaurus with no updates, adding WHO-DD preferred term for use in the relevant tabulation. Counts and percentages for prior and concomitant medications will be summarized by preferred term, treatment group and overall for the mITT population.

The number and percentage of subjects with intracranial and extracranial surgery will be summarized by surgery type, actual surgical procedure (for example, craniofacial surgery), treatment group and overall for the mITT Population.

9.4 Demographic and Baseline Characteristics

Demographic variables (age, sex, ethnicity and race), pregnancy testing, and baseline characteristics (geographical region, GCS motor score, pupillary response, presence of hypoxia, presence of hypotension, classification of CT scan, presence of traumatic subarachnoid hemorrhage) will be summarized for each treatment group and overall.

The cause of TBI and type of injuries (face, chest, abdomen, extremities, spine, head injury alone) will be summarized by treatment group and overall.

Medical histories will be coded using Medical Dictionary for Regulatory Activities (MedDRA) version 13.0 with no updates. The number and percentage of subjects reporting any medical history will be displayed together with the number and percentage of subjects having at least one medical history within each system organ class (SOC) and preferred term.

9.5 Efficacy Analyses

9.5.1 Primary Efficacy Analysis

The primary efficacy variable is GOS evaluated at 6 months post injury. The primary analysis will be based on imputation of missing data as described in Section 5.

9.5.1.1 Proportional Odds Model

The primary efficacy variable of GOS at 6 months post injury will be compared between treatment groups using a POM. For the purposes of this analysis the first two categories of the GOS will be combined (vegetative state and dead). A POM will be fitted including the effect of treatment, geographic region (North America, Europe, Asia, and South America), age, GCS motor score, pupil response, and CT classification. With 4 categories in the response variable, GOS at 6 months following injury, the POM simultaneously fits 3 (number of categories – 1) binary logistic regression models as follows.

If $Y = \text{response} = \text{GOS at 6 months following injury}$.

Model 1

$Y_1 = 0$ (not event), if $Y = \text{vegetative state or dead}$
 $Y_1 = 1$ (event), if $Y = \text{severe disability, moderate disability, good recovery}$

Model 2

$Y_2 = 0$ (not event), if $Y = \text{vegetative state or dead, severe disability}$
 $Y_2 = 1$ (event), if $Y = \text{moderate disability, good recovery}$

Model 3

$Y_3 = 0$ (not event), if $Y = \text{vegetative state or dead, severe disability, moderate disability}$
 $Y_3 = 1$ (event), if $Y = \text{good recovery}$

The dichotomous logistic regression models for Y_J ($J=1, 2, 3$) can be expressed as follows:

$$\ln(P_J/(1 - P_J)) = \alpha_J + \beta_1 X_1 + \beta_2 X_2 + \beta_3 X_3 + \beta_4 X_4 + \beta_5 X_5 + \beta_6 X_6,$$

where

- \ln is the natural logarithm,
- P_J = Probability of an ‘event’ (for example, good recovery) = Probability that $Y_J = 1$,
- $P_J/(1 - P_J)$ = odds of an ‘event’,
- X_1 = treatment group,
- β_1 = effect of treatment,
- X_2 = region,
- β_2 = effect of region,
- X_3 = age,
- β_3 = effect of age,
- X_4 = GCS motor score,
- β_4 = effect of GCS motor score,
- X_5 = pupil response,
- β_5 = effect of pupil response, and
- X_6 = CT classification,
- β_6 = effect of CT classification.

With a POM, it is assumed that the effect of the explanatory variables, such as treatment, are identical for all possible dichotomies of the response variable, that is, β_1 , etc. are the same for each model.

The fact that the effects of the explanatory variables (e.g. treatment (β_1), etc.) are the same for each model is referred to as the proportional odds assumption and needs to hold for this methodology to be appropriate. This assumption will be tested using the Score Test. A non-significant result (p-value > 0.05) supports the assumption of proportional odds. As the Score Test is known to be anti-conservative, additional graphical methods will be used to assess the proportional odds assumption in greater detail, if the Score Test is statistically significant.

The proportional odds assumption for an ordinal response implies that the curves on the various cumulative logits are parallel. This assumption can be assessed visually for a given predictor (e.g. region) by plotting it against the empirical logits.

For the 4 levels of the GOS there will be 3 cumulative logits which can be expressed as:

$$\begin{aligned} \text{Logit}_1 &= \log[p_1/(1-p_1)] = \log[p_1/(p_2+p_3+p_4)] , \\ \text{Logit}_2 &= \log[(p_1+p_2)/(1-(p_1+p_2))] = \log[(p_1+p_2)/(p_3+p_4)] , \\ \text{Logit}_3 &= \log[(p_1+p_2+p_3)/(1-(p_1+p_2+p_3))] = \log[(p_1+p_2+p_3)/(p_4)] \end{aligned}$$

where $p_i = P(Y=i)$, where Y (response, GOS at 6 months) = i and i=1, 2, 3 or 4.

By using the observed counts, y_i , in the study data empirical logits can be computed for use in plots as follows:

$$\text{EmpLogit}_1 = \log[(y_1)/(y_2+y_3+y_4)]$$

where y_i =number of subjects with Y (response, GOS at 6 months) = i and i=1, 2, 3 or 4.

The empirical logits can then be calculated for each category of the predictor and plotted. If the resulting plotted lines are roughly parallel this can be considered a visual confirmation of the proportional odds assumption.

See Appendix 3 (Model Checking Figures) for plot specification details.

Provided that the proportional odds assumption is not rejected, the POM will then be used to test the null hypothesis that the odds of being “higher” or “lower” on the outcome variable, GOS at 6 months following injury, across the entire range of the outcome, adjusted for region, age, GCS motor score, pupil response, and CT classification (as defined in Section 4.3) is the same in both treatment groups, i.e.

Null Hypothesis:	$H_0 : \beta_1 = 0$
Alternative Hypothesis:	$H_1 : \beta_1 \neq 0$

If the p-value from the test of the null hypothesis of $\beta_1 = 0$ is less than 0.0003 (at the interim) or 0.0098 (at the final analysis), it will be concluded that BHR-100 is statistically significantly different from placebo with respect to the GOS at 6 months following injury. The odds of some degree of improvement in the GOS at 6 months will be modeled and the corresponding common odds ratio for treatment, e^{β_1} , can then be interpreted to determine the direction of the treatment difference as follows. With the placebo group being considered as the reference category, if the odds ratio (OR_{BHR-100/placebo}) is greater than 1, the odds of some improvement in the GOS at 6 months is greater in the BHR-100 treatment group compared to placebo.

In the event that the primary efficacy analysis does not show statistical significance at the study-wise 1% significance level, please refer to section 9.5.1.4 for further details on how the statistical significance of the primary efficacy analysis should be interpreted.

The POM will be fitted in SAS[®] using the PROC LOGISTIC procedure.

Goodness of fit of the model will be assessed using the Deviance and Pearson tests (add SCALE = NONE AGGREGATE to the MODEL statement of PROC LOGISTIC) to compare the fitted model with the saturated model. If these tests are not statistically significant it implies that the model fits the data adequately.

The score test for the proportional odds assumption and individual p-values associated with the tests of effects (treatment, geographic region, age, GCS motor score, pupil response, and CT classification) will be summarized for the POM of GOS at 6 months post injury.

The odds ratios and associated 95% CIs for the levels of the effects relative to a reference category will be presented for all factors and covariates included in the POM of GOS at 6 months post injury.

In addition to the results of the hypothesis tests from the statistical modeling, the number of non-missing observations, absolute and relative frequency (n and percentages), will be provided by treatment group for the GOS categories at 6 months post injury.

The analyses above will be repeated for the straight observed case analysis (no imputation of 6-month GOS or covariates) in the mITT population, the straight observed case analysis in the PP population (no imputation of 6-month GOS or covariates), and the analysis of imputed missing values in the mITT population for US subjects only.

In addition to the above POM for the primary analysis, the individual binary logistic regression models will be fitted for each possible dichotomization of the GOS at 6 months, as outlined above under model 1, 2 and 3. This will be done using missing value imputation for the mITT population. This will allow an assessment of the odds ratio for treatment within each possible dichotomization and a further assessment of the proportional odds assumption. If the parameter estimates obtained under each dichotomized model are similar then the proportional odds assumption would seem sensible.

A bar chart illustrating the percentage of responses in each GOS category for each treatment group will be produced for the GOS at 6 months for the mITT (observed values and missing values imputed) and PP populations (observed values).

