8. STATISTICAL PLAN

8.1 Sample Size Justification

It is planned to recruit a total of 1180 patients randomized in a 1:1 ratio to BHR-100 or placebo (590 in each treatment group). This sample size estimation is based on the use of a proportional odds model ([Whitehead, 1993](#)) to analyze the primary outcome variable, namely the conventional 5-point GOS at six months after injury. Assuming approximately 31% good outcome, 21% moderate disability, 19% severe disability and 29% combined vegetative state and death, the total sample size of 1180 subjects will give 90% power to detect a common odds ratio of 1.5 of improvement in outcome (i.e. 10% effect size) at the 1% significance level (two-sided). The baseline outcome distribution used is based on the six-month GOS outcome distribution from the head injury population with GCS 3-8 in the previous TBI Phase 3 trials in the International Mission for Prognosis and Analysis of Clinical Trials in TBI Project (IMPACT) Database ([Marmarou et al., 2007](#)).

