3.1 Sample Size Considerations

The primary efficacy measurement for this study is GOS at 6 months after injury; see section 4.1.

For the purposes of the analysis and sample size calculation, the first 2 categories of the GOS (vegetative state and dead) will be combined. Based on the 6-month GOS outcome distribution from the head injury population with GCS 3-8 in the previous TBI Phase 3 trials in the International Mission for Prognosis and Analysis of Clinical Trials in TBI Project (IMPACT) Database, it is assumed that the following GOS responses will be observed at 6 months, in subjects treated with placebo: 31% good recovery, 21% moderate disability, 19% severe disability, and 29% vegetative state or dead (Lu, 2011).

A sample size of 1,180 subjects receiving study drug (590 in each treatment group) will be needed to detect a common odds ratio of 1.5, of improvement in GOS at 6 months in BHR-100 compared to placebo, at 90% power and a significance level of 0.01 (2-sided). This calculation used the sample size equation for comparing 2 groups of ordinal data using the technique of ordinal logistic regression proposed by Whitehead (1997).

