4.3 Predetermined Covariates and Prognostic Factors

A number of predetermined prognostic covariates have been defined for consideration within this study:

- Age,
- Motor response component of GCS (1-2, 3, 4, or 5-6) used to determine eligibility,
- Pupillary response (bilateral, unilateral/no reactive pupils/not testable) used to determine eligibility,
- Presence of hypoxia (yes/suspected, no/unknown) any time prior to randomization,
- Presence of hypotension (yes/suspected, no/unknown) any time prior to randomization,
- CT result at baseline (Marshall's CT Classification I/II, III, IV, or evacuated/non-evacuated mass lesion),
- Presence of traumatic subarachnoid hemorrhage (yes, no), and
- Region (North America, Europe, Asia, South America).

All covariates will be measured at baseline, prior to randomization.

Randomization is expected to balance covariates amongst the treatment groups; consequently, no formal testing of baseline comparability will be conducted.

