When the primary efficacy endpoint is missing, the last observation carried forward (LOCF) principle will be used to populate the primary endpoint, i.e. the Month 3 GOS assessment will be carried forward. In the event that a subject is lost to follow-up and has neither the 3 nor the 6-month GOS, the missing values will be imputed based upon the primary proportional odds model (POM).

To obtain values for the missing responses using the POM the predicted response probabilities will be used. Specifying the PREDICTED option on the OUTPUT statement of PROC LOGISTIC, 3 (number of categories in response variable – 1) predicted probabilities will be provided for each subject; these are the ordered cumulative probability of each response category, i.e.

$$\text{Probability}(Y \leq 1) = P(Y=1) = \text{Probability GOS}=1$$

$$P(Y \leq 2) = \text{Probability that GOS is 1 or 2}$$

$$P(Y \leq 3) = \text{Probability that GOS is 1, 2 or 3}$$

Therefore, to obtain the predicted probability of each individual response, for example, the probability that the response was GOS=2, the following calculation is performed:

$$P(Y=2) = P(Y \leq 2) - P(Y \leq 1)$$

Similarly,

$$P(Y=3) = P(Y \leq 3) - P(Y \leq 2)$$

and finally,

$$P(Y=4) = 1 - [P(Y \leq 3)]$$

since the individual probabilities must sum to one.

The missing GOS response will then be set to the most probable category, i.e. the response with the largest predicted probability.

It is anticipated that there will be minimal missing data, however sensitivity analyses will be carried out to confirm that the imputation method(s) did not have an impact on the primary efficacy analysis results. Therefore, the primary efficacy analyses will also be conducted on observed values only, without any imputation.

Covariates, missing data imputation

For the primary efficacy analyses, missing data for the following covariates will be imputed as the most commonly occurring value over subjects with non-missing data: motor response component of GCS, pupillary response, presence of hypoxia, presence of hypotension, CT classification, and presence of traumatic subarachnoid hemorrhage.

GOS assessment – Dead responses

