9.5.1.2 Alternate Primary Efficacy Analysis (Sliding Dichotomy)

If the proportional odds assumption cannot be justified, a sliding dichotomy of the GOS outcome at 6 months following injury, following categorization of subjects into different prognosis groups (worst, intermediate, and best) based on baseline prognostic factors, will be the primary efficacy analysis. The primary sliding dichotomy analysis will be based on imputation of missing data (covariates and 6-month GOS assessments).

For each subject a baseline prognostic risk score (BPRS) will be calculated as a weighted linear function of baseline prognostic factors of age, age squared, GCS motor score, Marshall CT classification, pupillary reactivity, presence of hypoxia, presence of hypotension, and presence of traumatic subarachnoid hemorrhage. The weighting of the BPRS factors will be based on the prognostic model developed in Hukkelhoven et al (2005). The BPRS will be sorted from lowest to highest, noting that higher BPRS represent a worse prognosis, and split into tertiles which will represent best, intermediate and worst prognosis.

For the cohort predicted to have the worst outcome, the outcome of severe disability or better is considered a “favorable outcome,” while for the cohort predicted to have the best outcome, only the outcome of good recovery is considered a “favorable outcome.” For the middle cohort there is no difference from the dichotomized model, so that the outcomes of moderate disability and good recovery are pooled to define “favorable outcome.”

The hypothesis that the proportion of favorable responses observed in each treatment group is the same will be tested using the Cochran-Mantel Haenszel (CMH) Chi-Square test, adjusted for region.

Null Hypothesis: $H_0: p_1 = p_2$
Alternative Hypothesis: $H_1: p_1 \neq p_2$

where p_1 = proportion of favorable responses in the BHR-100 treated group and p_2 = proportion of favorable responses in the placebo treated group. The Mantel-Haenszel estimate of the common odds ratio and corresponding 95% CI will also be presented.

If the p-value from the test of the null hypothesis of $p_1 = p_2$ is less than 0.0003 (at the interim) or 0.0098 (at the final analysis), it will be concluded that there is a statistically significantly difference in the proportion of favorable responses between the 2 treatment groups.

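### The primary proportional odds model omits hypoxia, hypotension and traumatic subarachnoid haemorrhage, which the SAP lists as prognostic and already collects, at a small to modest cost in power

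*SAP*

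**What the plan says.** The SAP's primary model (9.5.1.1) is specified as follows: "A POM will be fitted including the effect of treatment, geographic region (North America, Europe, Asia, and South America), age", then GCS motor score, pupil response and CT classification. Protocol 8.3 gives the same terms.

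SAP 4.3 lists eight predetermined prognostic covariates for consideration. Five are in the model. The other three are hypoxia, hypotension and SAH, the last entered as "Presence of traumatic subarachnoid hemorrhage (yes, no), and". Section 4.3 states that all covariates are measured before randomization.

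The three appear in other places:
- SAP 5, on missing covariates: "For the primary efficacy analyses, missing data for the following covariates will be imputed as the most commonly occurring value". The list that follows includes all three.
- SAP 9.5.1.2, the sliding dichotomy that becomes primary if proportional odds fails. Its baseline risk score uses age, age squared, motor score, CT class, "pupillary reactivity, presence of hypoxia, presence of hypotension, and presence of traumatic subarachnoid hemorrhage".
- SAP 9.5.1.6, the exploratory model, where they are candidates for backward selection.

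Neither document says why the primary model uses the shorter list.

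**The concern.** The SAP treats these factors as prognostic, collects them at baseline and has a rule for missing values, but does not use them in the test that decides the trial. In a proportional odds model, leaving out a prognostic baseline covariate pulls the treatment odds ratio towards 1 and lowers power, even under perfect randomization. Adjusting for it needs no extra patients or data and does not disturb type I error.

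Power matters at the smaller effects the SAP itself considers: Table 3 gives 39.36% final power at a common odds ratio of 1.27. No planned analysis fits the full listed set as a fixed model. The exploratory model selects terms from the data at the 0.10 level and does not impute covariates. The other covariate sensitivity analysis, in Tables 14.2.1.13 and 14.2.1.14, is unadjusted.

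**Working it through.** **1. The plan's own figure.** Inputs from Protocol 8.1 and SAP 3.1: "the total sample size of 1180 subjects will give 90% power to detect a common odds ratio of 1.5 of improvement in outcome", "at the 1% significance level (two-sided"; placebo distribution "31% good recovery, 21% moderate disability, 19% severe disability, and 29% vegetative state or dead".

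An odds ratio of 1.5 gives a treated distribution of 40.3 / 21.6 / 16.7 / 21.4%. The averages over the arms are 0.356, 0.213, 0.178 and 0.252, and their cubes sum to 0.0766.

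N = 12(2.576 + 1.282)² / [(ln 1.5)² × (1 − 0.0766)] = 178.55 / (0.1644 × 0.9234) ≈ 1176.

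The stated 1180 is reproduced. The formula has no covariate terms, so the sample size does not depend on the omitted factors.

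**2. Effect of adding the three factors.** The documents give neither effect sizes nor prevalences, so these are assumptions: 1180 patients, marginal odds ratio 1.5, planned covariates as a linear predictor with SD 1.0, 4,000 simulated trials per scenario. Effective sample size gain = (z₂/z₁)² − 1, where z₁ and z₂ are the mean treatment z-statistics without and with the three factors.

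| Assumed ORs (hypoxia / hypotension / SAH) | Prevalence | z₁ | z₂ | Gain | Gain × 1180 | Simulated power |
|---|---|---|---|---|---|---|
| 1.3 / 1.3 / 1.3 | 20/20/50% | 4.402 | 4.429 | 1.2% | 14 | 96.5 to 96.7% |
| 1.5 / 1.7 / 1.7 | 20/20/50% | 4.378 | 4.473 | 4.4% | 52 | 96.8 to 97.1% |
| 2 / 2 / 2 | 25/25/50% | 4.340 | 4.536 | 9.2% | 109 | 96.2 to 97.4% |

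A repeat simulation under the same assumed effects gave gains of about 1%, 4% and 8%, with type I error near 1%.

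**3. Power points depend on the base.** SAP 9.5.1.1 declares significance if the p-value "is less than 0.0003 (at the interim) or 0.0098 (at the final analysis"; the final critical value is 2.58.
- *Marginal odds ratio 1.5.* The planned model is already above 96%, so the gains are 0.2, 0.3 and 1.2 points.
- *Odds ratio 1.27.* Scale each z by ln 1.27 / ln 1.5 = 0.5895. Then z goes from 2.595 to 2.611, from 2.581 to 2.637 and from 2.558 to 2.674. With power = Φ(z − 2.58), this is 50.6 to 51.2%, 50.0 to 52.3% and 49.1 to 53.7%, or 0.6, 2.2 and 4.6 points.
- *Odds ratio 1.5 conditional on all covariates.* A second simulation (1,500 trials per scenario; prevalences 20/15/60%; log odds ratios from about 0.25–0.3 to 0.7–0.9; planned-covariate SD 0.8–1.2) also included age squared. Power rose from 86.1 to 87.2%, 82.2 to 85.1% and 78.0 to 83.5%. Because age squared contributes, 5.5 points overstates the high case for three factors. Applying the z-ratios from step 2 to its planned-model z values (3.683, 3.543, 3.340) gives 86.5 to 87.0%, 83.2 to 85.1% and 77.6 to 81.9%, or about 0.5, 1.9 and 4.2 points. This mixes two sets of assumptions and is a rough guide.

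**4. Where the gain comes from.** In the middle scenario of the second simulation (marginal odds ratio 1.5), the standard error of the treatment log odds ratio rises from 0.1108 to 0.1122 while the mean estimate moves from 0.492 to 0.514. The ratio improves; the standard error does not.

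**5. Score test.** With four outcome categories, the test has 2 degrees of freedom per slope. Planned slopes: treatment 1, region 3, age 1, motor score 3, pupils 1 (binary, as in SAP 4.3), CT class 3. That is 12 slopes, or 24 degrees of freedom. Three binary factors make 15 slopes, or 30.

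**The case against.** The strongest reply is that this is a deliberate, prespecified choice. Protocol and SAP agree on the terms. The protocol synopsis, under baseline data analysis, ranks age, motor score, pupils and CT class as the leading prognostic factors, and all four are in the model. Section 4.3 lists covariates only for consideration. The planned covariates already bring most of the gain: with the marginal odds ratio at 1.5, the second simulation put unadjusted power at 88–90% and the planned model at 95–98%. All of this stands, and it is why the remaining gain is small to modest.

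A reader might infer that SAP 5 shows the three factors were meant for the primary model and then forgotten. It does not: the rule refers to primary analyses in the plural, and the sliding dichotomy's risk score needs these values. A reader might also infer that the fallback conditions on more prognosis than the primary model. It does not: the score only sorts patients into tertiles that set the favourable cut-point, and the overall Cochran-Mantel-Haenszel test adjusts for region alone.

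Added terms also have a price. SAP 9.5.1.1 makes the primary model depend on a score test that it calls anti-conservative, and more slopes give it more ways to reject. Unknown hypoxia or hypotension is coded as no, which would dilute any gain. The interim analysis uses the same model. These points shape the remedy but do not remove the gain.

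**Conclusion.** The omission is real and unexplained. Its cost is power: about 1% to 9% in effective sample size, from under 1 to about 5 power points. The range rests entirely on assumed effects and prevalences; the documents supply none, and the upper end needs all three odds ratios near 2.

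The documents do not support stronger readings. The planned test is not biased, its type I error is not affected, and the sample size stands. The gain should not be called precision, because the standard error rises slightly and the conditional odds ratio being estimated changes slightly. Age squared is not a listed covariate that was dropped; it belongs only to the risk score. This is a cheap improvement to a sound analysis.

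**What to change.** First establish whether the interim analysis has been run; the documents do not say.

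- **If it has not:** before unblinding, add hypoxia (yes/suspected versus no/unknown), hypotension (same coding) and traumatic SAH (yes/no) to the model in SAP 9.5.1.1, and to the logistic and Cox models that reuse its terms (9.5.1.1, 9.5.1.3, 9.5.3.1). Keep the five-covariate model as a prespecified sensitivity analysis.
- **If it has, with the five-covariate model:** keep that model as primary, so that interim and final tests concern the same conditional odds ratio, and prespecify the full-set model as the sensitivity analysis.

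Age squared is optional.

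Costs: three model degrees of freedom in about 1180 patients; six more on the score test; a slightly different conditional odds ratio; and continued coding of unknown hypoxia or hypotension as no. The model that imputes missing GOS also changes, since SAP 5 uses the primary model for this. Observed-case analyses, which do not impute covariates, may lose a few patients. The change must be declared in SAP 1.1 and handled under the special protocol assessment. No new data are needed.
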